#### **Details of the research program and clinical follow-up:**

- Patients that are referred for TMJ arthroscopy at our department will be asked if they agree to participate in the LOPO experiment. Patients will receive standard treatment in terms of hospitalization and examinations.
- Follow-up reviews will take place in our clinic.
- The initial follow-up period is six months.
- Patients may be invited for further follow-up visits as a routine practice in our department.

#### **Schedule and Flow Chart of the Experiment:**

- Recruitment of 10 Participants: we estimate that we can recruit 10 participants within a year. Notably, our department performs approximately 70 arthroscopic surgeries annually (70 patients per year).
- Data Summary: the data summarization process is expected to take less than 6 months.
- Publication: the results of the experiment will be published in an international scientific journal.

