As previously mentioned, the initial stage of the operation involves inserting the arthroscope into the rear part of the TMJ. This step is relatively straightforward because the proximity of the joint to the ear provides a visible landmark for the surgeon. The anatomical landmarks constituting the ear, eye, and cheekbone aid this approach. Conversely, inserting the working cannula into the front part of the joint is more challenging due to significant anatomical variation among individuals and lack of easy landmarks to rely on. Therefore, facial skin landmarks cannot reliably guide this insertion and the triangulation technique was described as an alternative. This technique involves creating a spatial relationship between three points: the arthroscope, the target area within the joint, and the working cannula's entry point. The term "triangulation" refers to the coordination between the visual axis of the arthroscope and the working cannula's path. The surgeon uses the arthroscope to guide the working cannula to the correct position within the joint. Successful insertion of the working cannula hinges on three conditions: 1) ensuring it avoids damaging nearby vital structures both during and after insertion, 2) positioning it directly within the arthroscope's field of view in the front part of the joint for immediate visibility, and 3) achieving successful insertion on the first attempt, with a maximum allowance for additional 1 or 2 attempts if necessary.

Successful arthroscopy relies on accurately placing the working cannula ideally on the first attempt, and at most on the second or third attempts. Multiple attempts to insert the cannula can lead to puncturing of the joint capsule, causing leakage of the irrigation fluid (saline) and swelling of the face. This edema not only discomforts the patient but also compromises sufficient inflation (hydro-distension) of the joint cavity, thereby complicating the surgical procedure. Scientific literature generally advises halting the procedure after few unsuccessful attempts to insert the working cannula into the correct position.

Furthermore, repeated attempts increase surgical risks, including potential damage to facial nerve branches, blood vessels in the face, and the auditory canal, as well as heightened post-operative pain.

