### **The total number of participants and how they will be recruited:**

The experiment will be carried out in the Department of Oral and Maxillofacial Surgery at Sheba Tel Hashomer Medical Center.

Up to 10 participants are needed to demonstrate that the LOPO device effectively positions the working cannula regardless of anatomical variation among individuals.

Candidates for the procedure are patients diagnosed in our department with closed lock, Wilkes stage 3, based on anamnesis, clinical examination, and imaging, for whom TMJ arthroscopy is the accepted treatment. These patients will receive the standard preoperative explanation about the procedure, including its course, expected results, potential risks, the necessity for post-operative physical therapy, and the requirement to avoid hard foods for a month after arthroscopy. Additionally, they will be informed about our intention to use the LOPO device and asked for their consent. Patients who consent to using the LOPO during surgery will receive a letter for their family doctor detailing the procedure and the device.

The patients will be treated using the standard arthroscopic tool set available at Sheba, along with the LOPO device we developed.

Participants will not receive any financial compensation or other benefits. It will be explained that their participation contributes to scientific and medical advancements. Successful performance of the device in real patients will significantly advance the field of TMJ arthroscopy.

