#### **Criteria for inclusion, exclusion, and exclusion from the experiment:**

- Inclusion criteria:
  - o Diagnosis of lock-jaw (Closed lock of the TMJ, Wilkes stages 3) based on anamnesis, clinical, and imaging.
  - o Have not undergone surgical intervention in the TMJ in the past.
  - o Adult patients (over the age of 18), not pregnant, and of sound judgment.
- Exclusion criteria:
  - o Patients who are minors, pregnant, or lacking judgment.
  - o Previous surgical intervention of the TMJ.
- Criteria for exclusion from the experiment:
  - o Patients who will not complete post-operative follow-ups as planned.

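### Up to ten patients, with no rule for order of entry and no record of those not enrolled, cannot demonstrate that LOPO works regardless of anatomical variation

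*Protocol*

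**What the plan says.** Four parts of the Protocol bear on this.

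- **Purpose of the sample** (*The total number of participants and how they will be recruited*): "Up to 10 participants are needed to demonstrate that the LOPO device effectively positions the working cannula regardless of anatomical variation among individuals".
- **Why placement is hard** (*Background*): inserting the cannula at the front of the joint is more challenging "due to significant anatomical variation among individuals and lack of easy landmarks to rely on".
- **Recruitment** (*Schedule and Flow Chart of the Experiment*): "we estimate that we can recruit 10 participants within a year", set beside the statement that "our department performs approximately 70 arthroscopic surgeries annually".
- **Eligibility** (*Criteria for inclusion, exclusion, and exclusion from the experiment*): adults only, with "Diagnosis of lock-jaw (Closed lock of the TMJ, Wilkes stages 3) based on anamnesis, clinical, and imaging" and "Have not undergone surgical intervention in the TMJ in the past".

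Two further sections describe how patients are approached. *Details of the research program and clinical follow-up* has referred arthroscopy patients asked whether they agree to take part. *Participant Privacy and Confidentiality of Collected Information* has lock-jaw patients needing arthroscopy offered the device, and sends those interested to their family doctor for advice. The same section describes one record: a spreadsheet of the names and results of up to ten patients.

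**The concern.** A statement that a device works whatever the anatomy needs a series that was not chosen on anatomy. By the Protocol's own account, anatomy drives the difficulty of placement, and so the attempts, time and failures listed under *Goals and Endpoints*. The department that developed the device also recruits the patients and expects it to do well. No bad faith is needed for a problem to arise: a surgeon starting with a new instrument may naturally begin with straightforward joints.

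If that happened, results would look better than in an ordinary run of eligible patients. With no record of who was eligible, asked, declined or passed over, no reader could tell. Such a record is hard to rebuild reliably later.

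A second problem does not depend on selection: ten patients, with no measure of anatomy among the outcomes, are too few for the claim.

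**Working it through.** **1. The plan's own figure.** The ten cannot be reproduced by calculation. The Protocol gives no expected failure rate, effect size, precision target, error rate or power.

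**2. Order of entry.** Set side by side, the two approach statements describe different groups: all patients referred for arthroscopy, and lock-jaw patients who need it. Neither says every eligible patient, or in order of presentation. Neither gives the surgeon discretion to choose. The spreadsheet covers enrolled patients only. Selection is therefore neither provided for, nor prevented, nor traceable.

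**3. Room for selection.** The ratio 10/70 = 14.3% uses total department volume. The eligible share is not stated, so I assume 25% to 100%:

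| Assumed eligible share | Eligible per year | Ten as a share of these |
|---|---|---|
| 25% | 17.5 | 57% |
| 50% | 35 | 29% |
| 75% | 52.5 | 19% |
| 100% | 70 | 14% |

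These shares are before refusals, so the true room for choice is unknown.

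**4. What a perfect result would show.** With 0 failures in n = 10, the exact upper limit on the failure rate is 1 − α^(1/n):

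- one-sided 95%: 1 − 0.05^(1/10) = 0.259, or 25.9%;
- upper end of the two-sided 95% interval: 1 − 0.025^(1/10) = 0.308, or 30.8%.

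These limits assume an unselected series.

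**5. Coverage of anatomy.** The chance that ten unselected patients include nobody with an anatomical type of prevalence q is (1 − q)^10. The Protocol gives no prevalences, so q is an assumption:

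| Assumed q | Chance the type is absent |
|---|---|
| 5% | 60% |
| 10% | 35% |
| 20% | 11% |
| 30% | 3% |

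**6. Feasibility of consecutive entry.** Months to fill ten places = 120 / (70 × eligible share × consent rate). With all 70 eligible and all consenting, 120/70 = 1.7 months. With 25% eligible and 50% consenting, 120/8.75 = 13.7 months. Of the combinations checked (eligible share 25%, 50%, 75% or 100%; consent 50%, 80% or 100%), only this last one exceeds the stated year.

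**The case against.** The strongest reply is that the Protocol already describes a general offer. Candidates are defined by diagnosis and consent, and no section lets the surgeon pick among them. That stands: selection of easy joints is a possibility left open, not something the plan sets up.

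Three stronger readings are tempting, and the documents do not support them.

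- *Ten are picked out of seventy.* The 70 are all arthroscopies. Entry is limited by diagnosis, age and earlier surgery, and then by consent. Ten in a year may reflect eligibility and uptake rather than choice.
- *Patients passed over become the comparison group.* *Method of Analyzing and Processing Results* speaks only of patients operated on without LOPO. It does not say whether they are concurrent or historical. If they are historical, steering hard joints into the comparison group does not arise.
- *The bias can be given a size.* One could assume 60–80% easy joints with 90% first-attempt success, and 50% in the rest. An unselected series then averages 74–82% against 90% for easy joints alone, a gap of 8–16 points. None of these rates is in the Protocol, and the sum supposes perfect sorting before surgery. Nothing in the text says difficulty can be predicted that well.

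It can also be said that screening logs are often kept in study-conduct documents, and that this is a small pilot. Both are fair. But the order of entry is a recruitment rule and belongs in the Protocol, and the sentence on what ten patients will demonstrate is stated there too strongly, whatever other documents contain.

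**Conclusion.** The point holds in a limited form. The Protocol rests a claim across anatomies on at most ten patients, does not fix the order in which eligible patients enter, and describes no record that would reveal selection. I put no figure on the bias from selection, because neither the eligible number nor success rates by difficulty are given.

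The firmer conclusion needs no assumption about selection. A flawless unselected series still leaves a failure rate of up to about 26% (one-sided) or 31% (two-sided limit), and a type with an assumed 10% prevalence would be missed 35% of the time. Consecutive entry is thus worth having but would not by itself rescue the claim; the wording must also be narrowed. The recruitment estimate is a feasibility statement and is not itself wrong.

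**What to change.** Make three changes before the first patient is enrolled.

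1. In the sections on recruitment, research program and privacy, use one consistent rule: *from the start date, every consecutive patient who meets the inclusion and exclusion criteria is offered LOPO until ten have been operated on, or the study is halted under its own halting conditions.*
2. Keep a log of eligible patients, showing who was asked, who declined and who was not offered the device, with reasons. Report it with the results.
3. Reword the purpose of the sample as a feasibility aim limited to the series obtained, with success and failure reported with exact confidence intervals. Drop the statement about anatomical variation.

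The cost is a few sentences and a short log. The sample size stays at ten, and the stated year suffices in all but the least favourable combination checked above. The downside is less freedom to choose early cases, though a patient may still be passed over with a recorded reason.

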**Participant Privacy and Confidentiality of Collected Information:**

- Patients diagnosed with lock-jaw who need TMJ arthroscopy will be offered the option to use the LOPO device during their surgery. They will receive an informational letter explaining the procedure and the use of the device.
- Interested patients should consult with their family doctor, presenting the explanatory letter for further advice. Regardless of their decision to participate in the trial, all patients will receive standard care in our department, including admission, hospitalization, discharge, and periodic follow-ups after surgery.
- A database containing the names of the patients (up to 10) and the experiment results (studied indices) will be maintained in an Excel sheet on a secure computer within the department.

**Conditions for Halting the Medical Experiment:**

- If the LOPO device does not perform as expected, based on its performance with anatomical models, its use will be halted immediately, and no further patients will be enrolled in the experiment.
- The use of the LOPO will also be immediately discontinued in the event of any known or unforeseen complications arising from the operation

**Reporting Unusual Events:**

- The researcher will promptly inform the Chair of the Helsinki Committee of Sheba Medical Center about any significant unusual events observed during the arthroscopy and the use of the LOPO device within one week. Additionally, any relevant new information related to these events will be communicated to the Helsinki Committee through subsequent follow-up reports.

**Method of Analyzing and Processing Results:**

- The data from the ten patients using the device will be compared with data from patients undergoing TMJ arthroscopy without using the LOPO device. The following parameters will be evaluated:
  - o Time elapsed from insertion of the working cannula until it is clearly visible through the arthroscope.
  - o Number of attempts made by the surgeon to correctly position the instruments within the joint cavity (limited to three attempts per surgery, following standard practice).
  - o Number of cases where the surgeon failed to correctly insert the working cannula, despite three attempts, as observed through the arthroscope.

- Measurements of maximal mouth opening of the patients undergoing the procedure, before as compared to after arthroscopy.

Contact:

[name]

Telepohone: [name]

Email: [[contact]](mailto:[contact]), [[contact]](mailto:[contact])

[name]

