#### **Technical details:**

- Manufacturer: Pollak Steinberg Ltd.
- Model: TMJ-DEVICE-100
- Materials: Stainless steel 303, resistant to autoclave sterilization, multi-use
- The device can be attached and detached from the arthroscope and working cannula at any stage of the operation.

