### **Goals and Endpoints**

This pilot study aims to recruit up to 10 patients to test the functionality of the LOPO in clinical conditions. The outcome of the study are:

1. The number of attempts required by the surgeon to correctly place the instruments in relation to each other within the joint cavity. No more than three attempts will be made in a single operation.
2. The time elapsed from the insertion of the working cannula until it is clearly visible by the arthroscope (measured in seconds).
3. The number of cases in which the surgeon fails to correctly insert the working cannula, meaning that after three attempts, the cannula is still not properly placed in the joint and not visible by the arthroscope.
4. The improvement of mouth opening after arthroscopy.

Our hypothesis is that the LOPO will shorten the duration of surgery by helping the surgeon insert the working cannula more quickly and easily. It should allow accurate insertion of the working cannula on the first attempt, reducing scuffing of tissues, fluid leakage, swelling, and surgical risks. Using the device does not increase the known risks of surgery.

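### The protocol names both comparison groups by whether LOPO was used, so an enrolled patient in whom it is given up before the first insertion has no sound place in the analysis

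*Protocol*

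**What the plan says.** The protocol sets the comparison under Method of Analyzing and Processing Results, where its opening sentence reads: "The data from the ten patients using the device will be compared with data from patients undergoing TMJ arthroscopy without using the LOPO device". Beyond this, the comparison group has no criterion; its source, period and size are not given.

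Enrolment works differently. Under Details of the research program and clinical follow-up, the protocol states: "Patients that are referred for TMJ arthroscopy at our department will be asked if they agree to participate in the LOPO experiment". The recruitment section adds: "Patients who consent to using the LOPO during surgery will receive a letter for their family doctor detailing the procedure and the device". Goals and Endpoints sets the ceiling: "This pilot study aims to recruit up to 10 patients to test the functionality of the LOPO in clinical conditions".

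Two sections allow for LOPO not being used throughout an operation. Technical details says: "The device can be attached and detached from the arthroscope and working cannula at any stage of the operation". Conditions for Halting the Medical Experiment says that if the device does not perform as expected, "its use will be halted immediately, and no further patients will be enrolled in the experiment". Neither says how the patient concerned is analysed. The only listed ground for removal from the experiment is "Patients who will not complete post-operative follow-ups as planned".

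Under Goals and Endpoints, outcome 1 is the number of attempts the surgeon needs, outcome 2 is the time from cannula insertion to a clear view, and outcome 3 is failure, where "after three attempts, the cannula is still not properly placed in the joint and not visible by the arthroscope".

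**The concern.** A patient joins the study by plan, but the analysis sentence describes the groups by what happened in theatre. The two differ for one kind of patient: enrolled, arthroscope placed, but LOPO not mounted or given up before the cannula is first inserted.

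Outcomes 1 to 3 do not register that event as a device failure. The clock starts at cannula insertion, and failure requires three unsuccessful attempts. What is recorded is whatever the surgeon then does freehand.

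The recruitment section says the participants are needed to show that LOPO positions the cannula effectively whatever the patient's anatomy. A patient whose anatomy or access defeats the device before insertion is a direct test of that aim. With at most ten patients, the handling of one such case is visible in the result.

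**Working it through.** The protocol gives no rate, effect size or derivation for its sample size on this point, so there is no figure of its own to reproduce. The check traces the affected patient through each reading of the text and then illustrates the size.

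**Tracing the patient (LOPO not used before the first insertion)**

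| Reading of the analysis sentence | LOPO group | Comparison group |
|---|---|---|
| Literal, by use | Patient is absent | Patient meets the only criterion |
| The ten enrolled | Patient is present, scored on the freehand attempts | Not barred by any stated rule |
| By plan, non-use scored as not achieved | Patient is present, counted against first-attempt LOPO placement | Patient is barred |

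Only the third row keeps the device failure in view, and the protocol does not state it.

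**Inputs for the illustration.** From the protocol: a maximum of 10 enrolled. All other counts are assumptions: LOPO is not used in 2 of the 10; 7 of the other 8 have first-attempt placement; the comparison group has 7/10 or, alternatively, 42/60 first-attempt placements (70% in both).

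**Case A: the 2 non-use patients need several freehand attempts.**
- By use, small comparison group: 7/8 = 87.5% against 7/(10 + 2) = 7/12 = 58.3%; difference 29.2 points.
- By use, larger comparison group: 87.5% against 42/(60 + 2) = 42/62 = 67.7%; difference 19.8 points.
- By plan: 7/10 = 70% against 7/10 or 42/60 = 70%; difference 0.

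The change on the LOPO side is 87.5 − 70 = 17.5 points. The change on the comparison side is 70 − 58.3 = 11.7 points with 10 comparators, but only 70 − 67.7 = 2.3 points with 60.

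**Case B: both non-use patients have a freehand first-attempt insertion.**
- Read as the ten enrolled: (7 + 2)/10 = 90% recorded, although LOPO achieved 7/10 = 70%.
- By use, small comparison group: 7/8 = 87.5% against (7 + 2)/12 = 75%; difference 12.5 points.

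**One patient only.** Suppose one of 10 enrolled patients cannot have LOPO used and the other nine succeed. By use, failures are 0/9 (exact 95% interval 0 to 33.6%). By plan, with non-use counted as failure, they are 1/10 (0.3 to 44.5%).

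**How likely is at least one such patient?** For an assumed non-use probability q per patient, the chance among 10 is 1 − (1 − q)^10: 40.1% for q = 5%, 65.1% for 10% and 89.3% for 20%. The documents give no value for q. If q is zero in practice, every reading gives the same result.

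**The case against.** The strongest reply is that the sentence is descriptive and lays down no rule. Ten is the enrolment target, so the ten patients it mentions can equally be the enrolled cohort, which is fixed by consent before surgery. No section removes a patient for non-use or moves one to the comparison group, and analysis sets are often defined in a statistical analysis plan, which is not shown here. This stands as far as it goes: the protocol does not order anyone to be reclassified. It does not remove the problem, because on the enrolled-cohort reading a freehand success is still credited to LOPO.

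A second reply is that misalignment is already scored. That is right where it shows up at insertion, since it then counts as an attempt, or as failure after three. The gap is limited to non-use before the first insertion. The statement that the device can be detached is a technical feature; it shows that this is possible, not that it is expected.

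A reader might go further and infer that failed cases would be replaced by easier ones until ten device users are reached. The documents do not support that. There is no replacement provision, recruitment is capped at 10, and the halting condition may stop enrolment once the device underperforms. Any illustration with more than ten planned patients would exceed the cap.

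**Conclusion.** The point holds as a fault of wording, at low severity. The protocol names its groups by use, enrols by plan, and has no rule that reconciles the two when LOPO is not mounted or is given up before the first insertion. On the literal reading the patient leaves the LOPO data and qualifies as a comparator. On the enrolled-cohort reading a freehand success can be scored as a LOPO success.

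In the illustration, two such patients in ten turn equality (70% against 70%) into an apparent LOPO advantage of about 29 points with 10 comparators, or about 20 points with 60. These sizes rest on assumed counts, including that both non-use patients need several freehand attempts, and on scoring non-use as not achieved. Most of the shift is on the LOPO side when the comparison group is large. It would be wrong to conclude that the comparison is certain to be biased: if LOPO is used in every enrolled patient, nothing changes.

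**What to change.** In the protocol's section Method of Analyzing and Processing Results:

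- Define the LOPO group as all enrolled patients (up to 10) in whom the arthroscope is placed with LOPO intended, including any in whom its use is halted under the halting conditions.
- Report non-use for a device or anatomical reason as first-attempt LOPO placement not achieved, and list the reason.
- State that enrolled patients never enter the comparison group.
- If wanted, add an analysis of patients in whom LOPO was actually used, labelled secondary.

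The cost is a few sentences and one line on the data sheet for use or non-use and its reason. The downside is that the LOPO success rate may look slightly less favourable. Nothing about the operation or the halting conditions needs to change.
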